6.10 Agent Destruction/Disposal

At the completion of investigation and after receiving approval to do so from the CPN Compliance Coordinator, all unused study agent will be returned to NCI, DCP Repository according to the DCP "Guidelines for AGENT RETURNS" and using the DCP form "Return Drug List".

7. CLINICAL EVALUATIONS AND PROCEDURES

7.1 Schedule of Events

Evaluation/ Procedure	Pre- Registration ¹	Screening/ Baseline ¹	Registration/ Randomization	Weekly (+/- 2 days)	Month 3 (+/- 7 days)	Month 6 or Early Termination (+/- 14 days)	Follow-Up – Month 7 (+/- 14 days) ²
Informed Consent	Х						
Assess Eligibility		X					
Medical History		X		2		3	
Physical Exam		X				X	
Alcohol and tobacco use assessment ⁶		Х				X	
Vital Signs (Ht, Wt, temp, pulse, BP)		х			Х	Х	
Laboratory Tests ³		X			X	X	
Stool antigen testing for H. pylori		х					
EGD with biopsies		X ⁴				Х	
Research blood collection		Х			X	Х	
Pregnancy test, if applicable ⁵		X	X				
Concomitant Medications		Х		Х	Х	Х	Х

Evaluation/ Procedure	Pre- Registration ¹	Screening/ Baseline ¹	Registration/ Randomization	Weekly (+/- 2 days)	Month 3 (+/- 7 days)	Month 6 or Early Termination (+/- 14 days)	Follow-Up – Month 7 (+/- 14 days) ²
Dispense Study Agent and Medication Diaries			Х		Х		
Collect/Review Study Agent and Medication Diaries					Х	Х	
Was It Worth It (WIWI) ⁶						Х	
Adverse Events	2			X	X	X	X
Telephone Contact				X			Х

- 1. Pre-Registration and screening must take place ≤ 28 days prior to registration/randomization.
- 2. In the case of early termination, the follow-up phone call will take place 30 days (+/- 14 days) after the completion of the post-intervention visit tests and procedures.
- 3. Laboratory testing includes AST, ALT, Alkaline phosphatase, CBC (Platelets, Hemoglobin, WBC), BUN, Total bilirubin, Creatinine.
- 4. Eligibility will be determined based upon local pathology review. Pathology report documenting eligibility will be placed in the participant's study file. Specimens or images will be sent for central pathology review at the University of Puerto Rico. Discrepancies will be reviewed and resolved by both pathologists on a case-by-case basis.
- A negative serum or urine pregnancy test (Individuals of childbearing potential only) must be documented ≤ 7 days prior to registration/randomization. If screening pregnancy test took place ≤ 7 days prior to registration/randomization, it does not have to be repeated.
- 6. Study participants may choose not to answer some or all of the questions on the assessments and questionnaire.

7.2 Baseline Testing/Prestudy Evaluation

7.2.1 Prescreening and Informed Consent

Participants will be identified by review of medical records and/or through implementation of the site recruitment plans. Potentially eligible participants will review the study events and risks in detail with site study team member and, if willing, sign the informed consent document. Participants will then be pre-registered and assigned a unique participant identification number.

7.2.2 Screening and Baseline

Initial screening will include a review of medical/surgical history, review of baseline symptoms, assessment of vital signs, physical examination, review of concomitant medications, and baseline alcohol and tobacco use assessment. If still eligible, blood will be drawn for clinical laboratory tests (AST, ALT, Alkaline phosphatase, CBC [Platelets, Hemoglobin, WBC], BUN, Total bilirubin, Creatinine) and for research. A stool antigen test will be performed to assess *H. pylori* infection. The participant will then undergo an EGD with biopsies (surveillance and research). Three sites (antrum, corpus, and incisura) will be biopsied (See Appendix D). Histologically-confirmed MAG, GIM, or both (at a minimum of one site) are required for eligibility and will be determined by the local pathologist. Specimen images will also be collected for central analysis. However, the results of the central review are not required prior to registration/randomization. Any discrepancies between the local and central pathologists will be resolved on a case-by-case basis by the two pathologists.

Screening/baseline activities must be completed ≤ 28 days prior to Registration/Randomization.

7.2.3 Registration/Randomization

Upon confirmation of eligibility, participants will be registered to the study and randomized to one of the two treatment arms. Participants will be dispensed a supply of study agent or placebo (200 capsules for 90 days), along with a medication/symptom diary and instructions for completion. Initiation of study agent (or placebo) must begin \leq 14 days following registration/randomization.

7.3 Evaluation During Study Intervention

Participants will be contacted by telephone weekly (+/- 2 days) to assess compliance. Adverse events and concomitant medications will also be assessed and recorded.

At least two weeks prior to the Month 3 visit, the data manager/nurse/pharmacist at the participant's institution must contact the CPN Registration Office at [contact] for code numbers to order additional study product for dispensing to the participant at the Month 3 visit.

At Month 3 (+/- 7 days), participants will return for a study visit, which will include an assessment of vital signs, safety and toxicity blood tests, adverse event and concomitant medications assessment. The study medication diary will be reviewed and collected. Any remaining study agent will be collected. A new study agent supply and medications diaries will be provided.

7.4 Evaluation at Completion of Study Intervention

The post-intervention evaluation will take place at Month 6 (+/- 14 days), or in the event of early termination. This evaluation will include assessment of adverse events and concomitant medications, follow-up alcohol and tobacco use assessment, WIWI questionnaire, a physical exam and assessment of vital signs, repeat safety/toxicity blood tests, a research blood collection, and repeat EGD with biopsies. Any individuals who discontinue intervention early for any reason will be encouraged to undergo the remaining tests and procedures as scheduled.

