5.7 Adherence/Compliance

5.7.1 Compliance will be defined as a study participant having taken 75% of the required doses. Weekly phone calls will be implemented to increase likelihood that participants comply with study instructions.

5.7.2 Compliance will be determined by participant report (medication diary) and tablet count after review by the site study coordinator. Compliance will be defined as ingestion of \geq 75% of the planned agent doses. The primary endpoint analysis will be based on the intent-to-treat principle, where all randomized patients that complete both the pre-intervention and post-intervention exams will be included. Secondary data analyses will include all randomized participants (i.e. adverse event analyses) or relevant subject subgroups (i.e. those who demonstrate \geq 75% compliance with the study agents), as appropriate.

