8.4 Off-Study Criteria

Participants may go "Off-Study" for the following reasons: development of an adverse event or serious adverse event, death, lost to follow-up, participant withdrawal, physician decision, protocol violation, complete study, or other (with detailed comments provided). Reason(s) will be noted in the participant's research records, with the primary reason clearly identified. The participant will be classified as (Off Study/Off Agent). Data submission and follow-up after participants are determined to be "Off-Study/Off-Agent" for specific situations is noted below:

A registered participant is deemed ineligible if the participant did not satisfy each and every eligibility criterion at the time of study entry, for example, identified based on an audit or through the case evaluation process.

- If participants received study intervention, on-study materials and all data up until the point of confirmation of ineligibility will be submitted.
- If participants did not receive study intervention, on-study materials must be submitted. No further data submission is necessary. No follow-up is required.

Major Treatment Violation: A registered participant is deemed as being in major treatment violation by the coordinating center, if the participant's very first treatment/intervention administration is so grossly administered in error, that the participant's data can no longer be used for the primary endpoint. These cases are typically rare.

 On-study material and all data up until the point of confirmation of a major violation must be submitted.

Cancel/Participant Withdrawal: A registered participant is deemed a cancel if he/she refuses the study or withdraws consent before any study intervention is given. On-study material must be submitted. The Off Study case report form must be submitted. No follow-up is required.

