With 22 evaluable participants per arm, this study yields 88% power to detect a mean decrease of 7 pg/mg protein or more in IL-1 β level in the Meriva® intervention arm compared to a mean decrease of 0.5 pg/mg protein in the placebo arm (from baseline to 6 months), with an overall 1-sided significance level of 0.05 (2 sample t-test, assuming the same standard deviation of 7.5 pg/mg protein in each arm). If the data are not normally distributed, we will use the Wilcoxon Rank-Sum test for the primary endpoint analysis.

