13.6 Reporting and Exclusions

All randomized participants who are evaluated at baseline and 6 months and have IL-1 β cytokine levels from those time points will be evaluable for the primary endpoint of this study using the modified intent-to-treat principle. We plan to over-randomize assuming 12% drop out within 6 months to ensure an adequate sample size in the primary analysis cohort. There will be

no imputation for missing data. A summary and listing of all major protocol violations will be provided. All details will be given in the final study report and/or manuscript. Participants lost to follow-up will be censored on the last date of assessment (or contact) and as appropriate for analyses that are dependent upon length of study participation.

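### The plan gives conflicting rules on when an early stopper has the single post-baseline EGD and on whether that biopsy counts as the 6-month primary endpoint

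*Combined protocol and SAP*

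**What the plan says.** **Timing of the EGD.** Section 7.4 opens: "The post-intervention evaluation will take place at Month 6 (+/- 14 days), or in the event of early termination". The schema agrees, and the schedule of events in 7.1 uses one column for Month 6 and early termination. Section 7.5 times the safety call from the early visit when there is one, so an early visit is clearly foreseen. The last sentence of 7.4 points the other way: "Any individuals who discontinue intervention early for any reason will be encouraged to undergo the remaining tests and procedures as scheduled". Section 8.3 encourages early stoppers to complete the post-intervention procedures where appropriate, subject to refusal, loss to follow-up and clinical contraindication, but gives no date. No second post-baseline EGD is scheduled.

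**Who is analysed.** Section 5.7.2 describes an intent-to-treat primary analysis "where all randomized patients that complete both the pre-intervention and post-intervention exams will be included". Section 13.6 defines the evaluable set as "All randomized participants who are evaluated at baseline and 6 months" who have IL-1β from those time points, calls this modified intent-to-treat, and rules out imputation. Section 13.8 repeats that definition. It then names early discontinuation of intervention as a reason for exclusion from sub-analyses, which have no role in the efficacy conclusion.

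**Power.** Section 13.4: "With 22 evaluable participants per arm, this study yields 88% power to detect a mean decrease of 7 pg/mg protein or more" in IL-1β on Meriva "compared to a mean decrease of 0.5 pg/mg protein in the placebo arm", "with an overall 1-sided significance level of 0.05", with SD 7.5 pg/mg in each arm.

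**The concern.** The sole primary endpoint is the change in mucosal IL-1β from baseline to 6 months, and each participant has one chance to supply the second value. If the EGD is done when agent is stopped, that chance is used. What happens next depends on which section is followed. Under 5.7.2 the early biopsy stands in for the 6-month value, whatever the exposure was. Under a literal reading of 13.6 and 13.8 the same person has no 6-month value and drops out.

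The first route mixes different exposure times into one endpoint. The second conditions the primary comparison on an event after randomization, such as stopping for an adverse event or noncompliance, whose frequency may differ between arms. With about 22 evaluable per arm, a few participants matter. Because both rules are in the document, the choice between them can be made after the values are known. Two sites could also time the EGD differently.

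**Working it through.** **1. The passages side by side**

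| Question | Reading A | Reading B |
|---|---|---|
| When is the EGD after early stopping? | At early termination: schema, 7.1, 7.4 first sentence, 7.5 | On the original schedule: 7.4 last sentence. No date: 8.3 |
| Does an early biopsy enter the primary analysis? | Yes: 5.7.2; 13.8 lists early discontinuation for sub-analyses only | No: 13.6 and 13.8, which require a 6-month value |

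No visit window or mapping rule says how an early value is to be assigned. A participant who stops agent and has the EGD at Month 6 satisfies both analysis definitions. The conflict concerns only those biopsied early.

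**2. Reproducing the plan's power**

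Inputs from 13.4: n = 22 per arm, difference δ = 7 − 0.5 = 6.5 pg/mg, SD = 7.5, one-sided α = 0.05.

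Noncentrality = δ / (SD × √(2/n)) = 6.5 / (7.5 × √(2/22)) = 6.5 / 2.261 = 2.87, with 42 degrees of freedom. Noncentral-t power = 88.2%, which matches the stated 88%.

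Attrition (13.3): 25 × (1 − 0.12) = 22. So the 22 is already net of 3 losses per arm.

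**3. If early biopsies count**

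No one is then lost for stopping early, so the relevant n is up to 25 per arm. With no early biopsies, noncentrality = 6.5 / (7.5 × √(2/25)) = 3.06 on 48 degrees of freedom, and power is 92%.

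Assumptions not in the documents: m of 25 Meriva participants are biopsied early and show a fraction f of the 6.5 pg/mg effect. With q = m/25:

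- δ′ = 6.5 × [1 − q(1 − f)]
- Meriva variance = 7.5² + q(1 − q) × [6.5(1 − f)]², averaged with the placebo variance 7.5²

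Example, m = 3 and f = 0: q = 0.12; δ′ = 6.5 × 0.88 = 5.72; Meriva variance = 56.25 + 0.1056 × 42.25 = 60.71; pooled SD = √[(60.71 + 56.25)/2] = 7.65; power = 83%.

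| m of 25 | f | δ′ (pg/mg) | pooled SD | Power |
|---|---|---|---|---|
| 0 | – | 6.50 | 7.50 | 92% |
| 2 | 0 | 5.98 | 7.60 | 86% |
| 3 | 0 | 5.72 | 7.65 | 83% |
| 2 | 0.5 | 6.24 | 7.53 | 89% |
| 3 | 0.5 | 6.11 | 7.54 | 88% |

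**4. If early biopsies do not count**

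Three losses per arm leave 22, and power is 88% as planned. Only losses beyond the allowance reduce it: 85% at 20 per arm and 82% at 18.

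**The case against.** Several points on the other side are sound.

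*Section 7.4 can be read coherently.* The first sentence may concern people who leave the study, and the last those who only stop agent. That reading is reasonable, but the terms are undefined and 7.1 and the schema do not draw the distinction.

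*Section 13 governs the analysis.* The endpoint is stated throughout as baseline to 6 months, and 5.7.2 sits under compliance. This favours 13.6, but 5.7.2 expressly describes the primary analysis. The 13.8 list of sub-analysis exclusions also suggests that early stoppers belong in the main set. Nor does the plan say whether 6 months includes the early-termination visit.

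*Dilution is not shown.* A reader might infer that early biopsies are known to weaken the contrast. The documents give no time course for IL-1β. A biopsy on the stop date could still reflect an on-agent effect, and a Month 6 biopsy taken off agent may show as little effect or less.

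*A larger power loss is tempting.* Placing 3 zero-effect early stoppers inside the 22 gives 77%. But the 22 is already net of the 12% loss, so this uses the same allowance twice unless the early stoppers come on top of planned losses.

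*Sections 8.3 and 8.4.* A reader might see a contradiction because 8.4 gives as possible off-study reasons "development of an adverse event or serious adverse event, death, lost to follow-up, participant withdrawal, physician decision, protocol violation", while 8.3 lists adverse events as a reason to stop agent with continued follow-up. The 8.4 wording is permissive and an adverse event can lead to either outcome, so the documents do not support that charge.

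**Conclusion.** The inconsistency stands on the text. The plan gives more than one time for the only post-baseline EGD after early stopping, and more than one rule on whether an early biopsy enters the primary analysis. It should be settled before the analysis.

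Its size is limited. Under the assumed 2 or 3 early biopsies in the Meriva arm, counting them gives power of 83% to 89%; excluding them within the allowance gives the stated 88%. If they keep half the effect, the two rules are nearly equal in power. Power therefore does not decide between them. The case rests on bias and pre-specification: one rule admits values from the wrong time, the other excludes people for a post-randomization reason, and the choice is open once data are seen. The number of early stoppers and their effect are assumptions. Neither the size nor the direction of any bias can be established from the documents.

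**What to change.** 1. Reconcile the schema, 7.1, 7.4, 7.5 and 8.3 so that stopping agent is distinguished from leaving the study. For those who stop agent, are willing, and have no clinical contraindication (the condition 8.3 already sets), the one EGD would follow the Month 6 ± 14 day schedule already in 7.4.
2. Align 5.7.2 with 13.6 and 13.8: the primary set is all randomized participants with IL-1β at baseline and within the Month 6 window, regardless of exposure. Use one label for this set.
3. Pre-specify that an IL-1β value from an EGD outside that window goes to a sensitivity analysis.

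The off-study reasons in 8.4 need no change, and decisions to stop agent are untouched.

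The cost is amendment wording, with no additional EGD. The analysis rule can still be fixed for participants already biopsied early. The downsides are that some early stoppers may not return at Month 6, so some loss related to stopping remains, and that an off-agent Month 6 biopsy may show a smaller effect. No gain in power is claimed.

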7.5 Post-intervention Follow-up Period

A follow up telephone call will take place at Month 7 (+/- 14 days). In the case of early termination, this phone call will take place 30 days (+/- 14 days) after the post-intervention visit. Adverse events will be assessed. If AEs are reported, the concomitant medications will also be assessed. Serious adverse events will be followed to resolution. All events will be assessed and treated according to institutional standards of good clinical practice.

7.6 Methods for Clinical Procedures

Participants will undergo EGD, after being NPO (Nothing Per Os) for a minimum of 6 hours. Preand post-procedure monitoring, administration of any sedation, and standard-of-care surveillance and biopsy collection will follow institutional clinical practice guidelines.

At baseline, eligibility will be determined in part by the histological confirmation of MAG, GIM, or both on at least one of the biopsies of the corpus, antrum, and incisura. The local pathologist's report will be used to confirm eligibility. Central pathological confirmation will be performed by the laboratories at the University of Puerto Rico. Specimen image submission for central review is described in Section 10.2.3.

At baseline and Month 6, research endoscopic biopsies will be collected for endpoint analysis. This will include one pass of the forceps with two bites of tissue at each of three sites (antrum, corpus, and incisura) will be collected for endpoint analyses. Research specimen processing is described in Section 10.2.4.

8. CRITERIA FOR EVALUATION AND ENDPOINT DEFINITION

8.1 Primary Endpoint

The primary endpoint of this randomized trial is to compare the absolute change in IL-1 β cytokine levels (measured by Luminex assay) in the gastric mucosa from baseline to 6 months among participants randomly assigned to receive either Meriva® or placebo. Statistical considerations regarding sample size and study power are based on this primary study endpoint (Section 13.4).

8.2 Secondary and Exploratory Endpoints

Secondary and exploratory endpoints are defined in Section 13.5.

8.3 Off-Agent Criteria

Participants may stop taking the study agent due to: completion of the planned intervention period, development of an adverse event or serious adverse event, inadequate agent supply, noncompliance, use of concomitant medications, medical contraindication, refusal, ineligibility (see Section 8.4), major treatment violation (see Section 8.4) or alternative treatment. Participants will continue to be followed, if possible, for safety according to the intended schedule of events (see Section 7).

Participants discontinuing the planned intervention prematurely will be encouraged to complete the Post-Intervention Evaluation tests and procedures as appropriate (if participant does not refuse, is not lost to follow-up, or unless it is clinically contraindicated). See Section 8.4 for further details as to data submission for participants deemed Ineligible after starting treatment or classified as a Major Treatment Violation (i.e., protocol requirements regarding intervention during the first week post-randomization were severely violated).

8.4 Off-Study Criteria

Participants may go "Off-Study" for the following reasons: development of an adverse event or serious adverse event, death, lost to follow-up, participant withdrawal, physician decision, protocol violation, complete study, or other (with detailed comments provided). Reason(s) will be noted in the participant's research records, with the primary reason clearly identified. The participant will be classified as (Off Study/Off Agent). Data submission and follow-up after participants are determined to be "Off-Study/Off-Agent" for specific situations is noted below:

A registered participant is deemed ineligible if the participant did not satisfy each and every eligibility criterion at the time of study entry, for example, identified based on an audit or through the case evaluation process.

- If participants received study intervention, on-study materials and all data up until the point of confirmation of ineligibility will be submitted.
- If participants did not receive study intervention, on-study materials must be submitted. No further data submission is necessary. No follow-up is required.

Major Treatment Violation: A registered participant is deemed as being in major treatment violation by the coordinating center, if the participant's very first treatment/intervention administration is so grossly administered in error, that the participant's data can no longer be used for the primary endpoint. These cases are typically rare.

 On-study material and all data up until the point of confirmation of a major violation must be submitted.

Cancel/Participant Withdrawal: A registered participant is deemed a cancel if he/she refuses the study or withdraws consent before any study intervention is given. On-study material must be submitted. The Off Study case report form must be submitted. No follow-up is required.

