13.7 Evaluation of Toxicity (secondary endpoint)

All participants will be evaluable for adverse events (AEs) from the time of their first dose of Meriva® or placebo. To evaluate the AE profiles associated with each arm, the maximum grade for each type of adverse event will be recorded for each participant and frequency tables will be reviewed to determine the overall patterns. The number and severity of adverse events (overall and by intervention group) will be tabulated and summarized. Grade 3+ adverse events will be similarly described and summarized separately. As per NCI CTCAE, toxicities are defined as adverse events that are classified as either possibly, probably, or definitely related to the interventional agent. Overall toxicity incidence, as well as toxicity profiles will be explored and summarized within and between the 2 intervention arms. Frequency distributions, graphical techniques, and other descriptive measures will form the basis of these analyses. In addition, we will review all adverse event data that are graded as 3, 4, or 5 and classified as either "unrelated or unlikely to be related" to the study intervention in the event of an actual association developing.

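### Section 8.4 does not require adverse event data after confirmation of ineligibility or a major treatment violation in dosed participants, although 8.3 keeps them in safety follow-up

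*Combined protocol and SAP*

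**What the plan says.** Section 8.4 sets the data rule for a participant found not to have met the entry criteria. If agent was taken: "If participants received study intervention, on-study materials and all data up until the point of confirmation of ineligibility will be submitted". For a major treatment violation: "On-study material and all data up until the point of confirmation of a major violation must be submitted". For ineligible participants who never took agent, the text is different: "If participants did not receive study intervention, on-study materials must be submitted. No further data submission is necessary. No follow-up is required".

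Section 8.3 includes ineligibility and major treatment violation among the reasons for stopping agent, and then says: "Participants will continue to be followed, if possible, for safety according to the intended schedule of events (see Section 7". For data submission in these two groups it defers to the next section: "See Section 8.4 for further details as to data submission for participants deemed Ineligible after starting treatment or classified as a Major Treatment Violation".

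On analysis, 13.7 says: "All participants will be evaluable for adverse events (AEs) from the time of their first dose of Meriva® or placebo". Section 5.7.2 says: "Secondary data analyses will include all randomized participants (i.e. adverse event analyses". Section 11.1.1 requires every adverse event after consent and baseline to go on the adverse event form, with no exception for either group.

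An adverse event is also a reason for stopping agent in 8.3, while the off-study reasons in 8.4 include "development of an adverse event or serious adverse event, death, lost to follow-up, participant withdrawal, physician decision".

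**The concern.** A site dealing with a dosed participant who has just been ruled ineligible is told by 8.3 to continue safety follow-up and to look in 8.4 for what to submit. Section 8.4 asks for nothing after the date of confirmation. Two sites could reasonably act differently, and one that submits nothing further has complied with 8.4.

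The groups concerned can be linked to risk. Anticoagulant use, for example, is an exclusion (4.2.6, 4.4.1) because of a theoretical interaction (5.4), so a dosed participant found at audit to be taking one is ineligible. A major treatment violation is a gross error in the first administration. Section 8.4 explains that status by the data being unusable for the primary endpoint, which is no reason to stop collecting safety data.

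At stake are the completeness of the first-listed secondary endpoint (safety) and the count used by the 13.7.1 suspension rule. An event that is not submitted leaves the numerator, while the participant remains in the denominator. Observed rates can then only be too low.

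**Working it through.** **Passages side by side, for a dosed participant in either group**

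| Section | Safety follow-up or data after confirmation |
|---|---|
| 8.3 | Follow-up continues on the schedule, if possible; data submission deferred to 8.4 |
| 8.4 | Data required up to confirmation; silent afterwards |
| 5.7.2 | All randomized participants in the adverse event analyses |
| 11.1.1 | All adverse events recorded, no exception |
| 11.2.2, 11.2.3 | SAE reports within 48 hours; at least possibly related SAEs followed to resolution; no exception |
| 13.7 | Evaluable from first dose; no end date stated |
| 13.7.1 | Counts related grade 3 or higher events, serious or not, by arm |

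The direct conflict is between 8.3 and 8.4. The conflict with 13.7 is implied, because that section fixes who is evaluable and from when, but not until when.

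**Which events can be missed.** Most grade 4 and 5 events would meet the SAE definition in 11.2.1 and come in by that route. Grade 3 in 11.1.3 also covers events that limit self-care without a hospital admission. Such an event need not be an SAE, yet it counts in 13.7.1 if at least possibly related. It depends on the ordinary adverse event data that 8.4 limits.

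**How many participants.** The plan gives no figure. Section 13.3 expects up to 12% non-evaluable from all causes: 0.12 × 25 = 3 per arm. Ineligible participants are only part of that, and 8.4 itself describes major violations as rare. The range used below is therefore k = 0 to 3 affected participants.

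**Effect on the suspension rule (illustration).** Inputs: the 2-of-first-10 criterion from 13.7.1; an assumed true rate p of related grade 3 or higher events; and the worst case that every such event in the k participants falls after confirmation, is non-serious and is never submitted. With m = 10 − k:

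P(at least 2 observed) = 1 − (1 − p)^m − m·p·(1 − p)^(m−1)

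At p = 0.20:
- k = 0: 1 − 0.8^10 − 10 × 0.2 × 0.8^9 = 1 − 0.107 − 0.268 = 0.624
- k = 1: 1 − 0.8^9 − 9 × 0.2 × 0.8^8 = 1 − 0.134 − 0.302 = 0.564

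| Assumed p | k = 0 | k = 1 | k = 2 | k = 3 |
|---|---|---|---|---|
| 0.10 | 0.264 | 0.225 | 0.187 | 0.150 |
| 0.20 | 0.624 | 0.564 | 0.497 | 0.423 |
| 0.30 | 0.851 | 0.804 | 0.745 | 0.671 |

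**Effect on the final safety table.** One participant whose only qualifying event is not submitted lowers an arm's reported proportion by 1/25 = 4 percentage points. At 25 per arm accrual is complete, so this figure concerns reporting, not suspension.

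**Design figures.** None depends on this point. The stated 88% power reproduces at 88.2% (difference 7 − 0.5 = 6.5, SD 7.5, 22 per arm, one-sided 0.05, two-sample t-test) and is unaffected.

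**The case against.** The strongest reply is that 8.4 sets what must be submitted and does not forbid more. It waives further data and follow-up expressly for undosed ineligible participants, and waives follow-up for those who cancel, but never for dosed ones. Section 8.3 keeps follow-up going, 7.4 encourages anyone who stops early to complete the remaining procedures, 7.5 provides a follow-up call, and 11.1.1 and 11.2 have no exceptions. This much stands: a reader might infer that 8.4 ends follow-up, or removes all later adverse events, and the documents do not support that. Serious events remain reportable. The reply does not close the gap for non-serious events, because 8.3 itself sends the reader to 8.4 for data submission and 8.4 asks for nothing after confirmation.

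A reader might also infer that 8.4 cuts off data for participants who leave because of an adverse event. It does not. Its data rules cover ineligibility, major violation and cancellation only, and the event that prompts leaving is recorded under 11.1.1. The fault there is narrower: the same reason sits in both lists without a statement of which follow-up applies.

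Nor can the loss be sized from the 30 days allowed in 6.8.2.3 for filing pathology reports. That is a filing deadline, not a check that finds ineligibility. Local review settles histology before randomization, and central review is done once, at study completion (10.2.3), normally after the adverse event data are in. The exposure comes mainly from the audits and case evaluation that 8.4 names.

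Finally, 12.4 refers to a study-specific monitoring plan that is not among the documents. It might give more detail, but it would not remove the contradiction in the protocol.

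**Conclusion.** The point holds for dosed participants later ruled ineligible or a major treatment violation. The data limit in 8.4 contradicts the continued safety follow-up in 8.3 and does not support the analysis set in 5.7.2 and 13.7. What can be lost is non-serious adverse events after confirmation, including related, non-serious grade 3 events that 13.7.1 counts.

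The effect is probably small. With one affected participant among an arm's first 10, the worst-case drop in the chance of meeting the 2-of-10 criterion is 0.04 to 0.06 for assumed event rates of 10% to 30%. With three affected it is 0.11 to 0.20, but three is the whole planned allowance for non-evaluable participants in an arm, all falling among the first 10. These figures rest on assumed event rates and on the loss of every qualifying event in those participants, so they are upper bounds for each k. With blinded assignment (6.9) there is no evident reason for the loss to fall more on one arm. The concern is under-reporting, not a predictable bias between arms.

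**What to change.** In 8.4, for participants who took at least one dose, replace the limit at confirmation (in both the ineligibility and the major violation items) with a requirement along these lines: on-study materials are submitted, and adverse event and SAE data continue to be collected and submitted on the schedule in 8.3 and Section 7, through the follow-up call in 7.5 where possible. The call keeps the timing that 7.5 already gives it. Add that these events count in 13.7 and in the 13.7.1 suspension rule.

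Because an adverse event appears both as an off-agent reason in 8.3 and as an off-study reason in 8.4, also state that the 8.3 safety follow-up applies to participants who stop for that reason.

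The cost is a wording amendment and a few extra calls and adverse event forms. Sample size and power do not change.
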